7.2. Number of Subjects

Up to approximately 133 subjects transitioned from Study 747-213 or Study 747-214 (or other Sponsor studies) who continue to meet this protocol's requirements.

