15.7. Handling of Missing Data

Subjects who discontinue investigational product are expected to continue in the study until study termination. Missing data will be assumed to be missing at completely random. No data will be imputed.

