9. EFFICACY ANALYSES

The efficacy endpoints of the study are defined below. Additionally, the planned analyses for these endpoints are described. All efficacy endpoints will be presented in by-subject data listings.

Missing data will be assumed to be missing at random. In order to determine the effect of missing data on the analysis, efficacy endpoints will be analyzed using different methods of imputation as described below.

During the conduct of the study, the DMC may recommend refining the missing data strategy to better address the observed pattern of missing data, based on blinded monitoring of the data.

All efficacy analyses will be summarized using descriptive statistics at Baseline and at each scheduled postbaseline visit. The change from baseline and percent change from baseline will also be summarized. Descriptive statistics, including change from baseline, percent change from baseline, and estimates of least-square (LS) means, SEs, and 95% CIs, will be presented.

Estimates of the mean difference between treatment groups, the SE of the difference, and 2-sided 95% CI of the difference will also be presented.

In efficacy analyses, subjects who do not provide an assessment at the specified timepoint for the defining of response will not be included. That is, for the percentage of responders, the subject will not be included in the numerator or the denominator.

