9.1. Efficacy Endpoints

The LTSE Population will be the population used for the efficacy analyses. Baseline is defined as the last assessment performed before the first dose of investigational product in Study 977-311, unless otherwise specified.

The efficacy endpoint at post-baseline site visits includes:

- Response rate of $\geq 40\%$ reduction from baseline and normalization rates of ALP
- Normalization rates of GGT, ALT, AST, total and conjugated bilirubin
- Change from baseline in GGT, ALT, ALP, AST, and total and conjugated bilirubin
- Percentage of subjects with ALP $< 1.67 \times \text{ULN}$, total bilirubin $\leq \text{ULN}$, and ALP decrease of $\geq 15\%$ from baseline
- Change from baseline in noninvasive markers of liver fibrosis, including liver stiffness measured by TE and ELF score
- Change from baseline in the GLOBE, UK-PBC, and MELD scores

All continuous and categorical additional endpoints will be summarized using descriptive statistics at baseline and at each scheduled post-baseline visit. No statistical inference will be done on those endpoints.

[figure not shown]
The intercurrent event in this study includes the use of prohibited medication and treatment discontinuation. Data collected after the intercurrent events, such as the use of prohibited medications, and data collected after treatment discontinuation will be included in the analyses (Treatment Policy Estimand).

The 5 attributes of the efficacy estimand are provided in Table 1.

[figure not shown]
Table 1: Attributes of Efficacy Estimand

[figure not shown]
Estimand Attribute	Elements
Population	All subjects with PBC who participated and are actively taking investigational product in Study 747-213 or Study 747-214 (or other Sponsor studies)
Treatment	OCA+BZF FDC Tablets
Efficacy Endpoint	All efficacy endpoints
Intercurrent Events	Use of Prohibited medication (Treatment Policy) Treatment Discontinuation (Treatment Policy)
Primary Efficacy Endpoint Population Level Summary	Descriptive summary in the target population

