11. DEVIATIONS FROM PROTOCOL

There have been no deviations between the protocol-defined statistical analyses and those presented in this statistical analysis plan.

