APPENDIX A. DATA PRESENTATION CONVENTIONS:

Unless otherwise specified, the baseline value for analyses of all parameters is defined as the last non-missing value prior to the first administration of investigational product.

For categorical variables, the number and percentage of subjects within each category of the parameter, including a category for missing data, will be presented. Percentage calculations will be based on the analysis population, unless otherwise specified.

For continuous variables, summary statistics will include the number of subjects and the mean, standard deviation (SD), standard error of the mean (SEM), median, 25th and 75th quartiles, minimum, and maximum values.

All statistical analyses will be performed using SAS statistical software Version 9.4 or higher unless otherwise noted.

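### Protocol and SAP missing-data rules conflict, and observed-case response rates with no rule for death or transplant may overstate long-term response

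*SAP*

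**What the plan says.** - **Protocol 15.7:** "Missing data will be assumed to be missing at completely random. No data will be imputed".
- **SAP 9, assumption and imputation:** data are taken as missing at random and, to gauge the effect of missing data, "efficacy endpoints will be analyzed using different methods of imputation as described below". No such method is visible after that sentence. The only imputations set out are for partial dates (SAP 5.2) and for laboratory results beyond quantifiable limits (SAP 5.3).
- **SAP 9, responder rule:** "subjects who do not provide an assessment at the specified timepoint for the defining of response will not be included", and this applies to numerator and denominator alike.
- **SAP 9.1 and SAP Table 1:** two intercurrent events are named, prohibited medication and treatment discontinuation, both under treatment policy; "data collected after treatment discontinuation will be included in the analyses (Treatment Policy Estimand". Death and liver transplant are not listed.
- **Protocol 7.4.3 (Table 5) and 8.4.1:** evaluation, listing or completion of a liver transplant ends investigational product permanently, and the subject goes on attending scheduled visits.
- **SAP 9, other content:** least-squares means are promised without a model (MMRM appears only among the abbreviations). So are "Estimates of the mean difference between treatment groups". The DMC may recommend changing the missing-data strategy after blinded monitoring. Protocol 9.4.1 and 9.4.2 and SAP 3.3 say that there are no treatment groups and that blinding does not apply.
- **Default denominators:** SAP 5 uses non-missing data; SAP Appendix A says "Percentage calculations will be based on the analysis population, unless otherwise specified".
- **SAP 11:** "There have been no deviations between the protocol-defined statistical analyses and those presented in this statistical analysis plan".

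**The concern.** The two documents make different assumptions about why data are missing and disagree on whether values will be imputed, yet the SAP says that nothing has changed. A programmer could not run the announced imputation analyses from the public text, nor estimate a treatment difference with one arm.

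The responder rule also decides whom a Month 24 or Month 60 rate describes. SAP Table 1 aims at a summary in the target population under treatment policy, but the rule summarizes attendees. A subject who dies has no later assessment and so drops out of every later rate without being counted as a failure. Over 60 months, dropout may plausibly follow poor tolerability or progression. If so, the remaining group responds better than the whole. With no control arm, nothing in the study would reveal the difference. For transplant the risk is of another kind: normal biochemistry from a graft could be scored as a drug effect.

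**Working it through.** **1. The rules side by side**

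| Item | Protocol | SAP |
|---|---|---|
| Assumption | missing completely at random (15.7) | missing at random (9) |
| Imputation | none (15.7) | several methods announced, none visible (9) |
| Subject unassessed at a visit | no separate rule | out of numerator and denominator (9) |
| Declared deviations | – | none (11) |

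The first two rows conflict, so the SAP 11 statement is incorrect. The third row is compatible with the protocol's rule against imputation.

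**2. Size of the observed-case effect**

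The plan has no figure to reproduce. The study size is a rollover count, "Up to approximately 133 subjects transitioned from Study 747-213 or Study 747-214 (or other Sponsor studies", and the documents give neither a dropout rate nor an expected response rate.

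Inputs:
- N = 133 (Protocol 7.2).
- Assumed: 10% to 40% missing at a visit; about 60% response among the observed; response rate q among the missing.

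With m missing, o = N − m observed and r observed responders:
- observed-case rate = r/o
- missing as non-response = r/N
- general rate = (r + q·m)/N
- overstatement by the observed-case rate = r/o − (r + q·m)/N = (m/N)·(r/o − q)

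| Missing | m | o | r | Observed-case r/o | q = 0: r/N | Gap (points) | q = 0.30: (r + 0.3m)/N | Gap (points) |
|---|---|---|---|---|---|---|---|---|
| 10% | 13 | 120 | 72 | 60.0% | 54.1% | 5.9 | 57.1% | 2.9 |
| 20% | 27 | 106 | 64 | 60.4% | 48.1% | 12.3 | 54.2% | 6.2 |
| 30% | 40 | 93 | 56 | 60.2% | 42.1% | 18.1 | 51.1% | 9.1 |
| 40% | 53 | 80 | 48 | 60.0% | 36.1% | 23.9 | 48.0% | 12.0 |

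Check at 30% missing and q = 0: (40/133) × (56/93) = 0.181, or 18.1 points.

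Over assumed observed response of 40% to 80% and 10% to 40% missing, the gap at q = 0 runs from 3.9 to 31.9 points. If q equals the observed rate, the gap is zero. If all 40 missing subjects were responders, the true rate would be (56 + 40)/133 = 72.2%, and the observed-case figure of 60.2% would be too low.

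**3. Transplant**

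No single sentence says that post-transplant values are kept. It follows from three statements: transplant ends treatment, scheduled visits continue (both Protocol 8.4.1), and data after discontinuation are analysed (SAP 9.1). One transplanted subject counted as a responder adds 1/133 = 0.75 points, or 1/93 = 1.08 points with 30% missing.

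**The case against.** Much of the case on the other side stands.

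- **Direction.** A reader might infer that long-term efficacy is biased upward. The documents do not show this. The bias needs missing subjects to respond less often than observed ones, and every rate above is an assumption.
- **Retention.** Subjects who stop product are asked to attend until Month 60 (Protocol 7.6 and 8.4), and their off-drug values are analysed. Failing subjects who stay therefore remain in the denominator and lower the rate. They are nonetheless free to leave (Protocol 8.4.2), and a subject who dies cannot be retained.
- **Baseline.** It is taken on parent-study treatment. A subject already at the 61.4% mean ALP fall reported for the combination arm of Study 747-214 would need a total fall of 1 − 0.386 × 0.6 = 76.8% to meet the 40% criterion. This pushes change-based response down, so the net direction is unknown. It is a separate matter: at a given endpoint and baseline, the comparison of attendees with all subjects is unaffected, and normalization rates do not use baseline.
- **Transplant.** A reader might infer that the plan deliberately scores grafts as successes. It does not say so, and Protocol 8.4.1 describes the later visits as safety follow-up. Protocol 8.3 excludes, among others, MELD above 12, bilirubin above normal and Child-Pugh 7 or more, so few cases are likely.
- **Denominators.** A reader might infer that SAP 5 and Appendix A leave the responder denominator undefined, or that protocol and SAP state opposite rules for responder rates. Neither holds. Both defaults yield to specific rules, SAP 9 gives one, and that rule agrees with no imputation.
- **Removed text.** SAP 9.2 has gaps, and 9.2.1.1 refers back to a MELD method that is not visible. Imputation methods may have been removed too. Only their absence from the public text can be stated.
- **Non-response as the main analysis.** This would score one skipped visit as a failure and bias rates downward when missingness is unrelated to outcome. It fits better as a pre-specified companion analysis.

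**Conclusion.** Should be fixed. The conflict between Protocol 15.7 and SAP 9, the incorrect statement in SAP 11, and the sentences that presuppose treatment groups or blinding rest on the text alone. So does the removal of deceased subjects from later denominators.

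The numerical effect is conditional. At an assumed 60% observed response and 30% missing, the observed-case rate is 60.2%. It compares with 42.1% if no missing subject responds and 51.1% if they respond at an assumed 30%. It is unbiased if missingness is unrelated to response. The transplant gap is real on a literal reading but probably small, at about 0.75 points per case over 133.

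A reader might infer that this undermines the study. It does not: the primary objective is safety, efficacy is descriptive, and no hypothesis or decision rule depends on these rates. In an estimation study, however, the estimate is the result, and its denominator should be settled in advance.

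**What to change.** 1. State one missing-data rule in Protocol 15.7 and SAP 9, and either write out the imputation methods or remove the sentence announcing them.
2. From death or liver transplant onward, score the subject as a non-responder for responder and normalization endpoints and keep the subject in the denominator. Exclude post-transplant values from continuous summaries. Enter both events in SAP Table 1, saying openly that the strategy differs between the two kinds of endpoint.
3. Report the observed-case rate with the number assessed at each visit. Beside it, report a pre-specified missing-as-non-response analysis over all LTSE subjects who could have reached the visit by the data cut.
4. Name the model for the promised least-squares means, for example a within-subject MMRM with visit and baseline.
5. Delete the treatment-difference sentence and the blinded DMC sentence from SAP 9, and correct SAP 11.

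The cost is SAP wording, a small edit to Protocol 15.7 and some extra analysis. The supporting rates will look somewhat less favourable. Protocol section 15 requires SAP approval before any snapshot, so this should be settled by then.

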9.1. Efficacy Endpoints

The LTSE Population will be the population used for the efficacy analyses. Baseline is defined as the last assessment performed before the first dose of investigational product in Study 977-311, unless otherwise specified.

The efficacy endpoint at post-baseline site visits includes:

- Response rate of $\geq 40\%$ reduction from baseline and normalization rates of ALP
- Normalization rates of GGT, ALT, AST, total and conjugated bilirubin
- Change from baseline in GGT, ALT, ALP, AST, and total and conjugated bilirubin
- Percentage of subjects with ALP $< 1.67 \times \text{ULN}$, total bilirubin $\leq \text{ULN}$, and ALP decrease of $\geq 15\%$ from baseline
- Change from baseline in noninvasive markers of liver fibrosis, including liver stiffness measured by TE and ELF score
- Change from baseline in the GLOBE, UK-PBC, and MELD scores

All continuous and categorical additional endpoints will be summarized using descriptive statistics at baseline and at each scheduled post-baseline visit. No statistical inference will be done on those endpoints.

[figure not shown]
The intercurrent event in this study includes the use of prohibited medication and treatment discontinuation. Data collected after the intercurrent events, such as the use of prohibited medications, and data collected after treatment discontinuation will be included in the analyses (Treatment Policy Estimand).

The 5 attributes of the efficacy estimand are provided in Table 1.

[figure not shown]
Table 1: Attributes of Efficacy Estimand

[figure not shown]
Estimand Attribute	Elements
Population	All subjects with PBC who participated and are actively taking investigational product in Study 747-213 or Study 747-214 (or other Sponsor studies)
Treatment	OCA+BZF FDC Tablets
Efficacy Endpoint	All efficacy endpoints
Intercurrent Events	Use of Prohibited medication (Treatment Policy) Treatment Discontinuation (Treatment Policy)
Primary Efficacy Endpoint Population Level Summary	Descriptive summary in the target population

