3. Male subjects who are sexually active with female partners of childbearing potential must agree to use a condom with spermicide and to use (or have their partner use) 1 other approved method of highly effective contraception from the initiation of the study and until at least 90 days after the last dose of investigational product as listed in Inclusion Criterion #2.
 4. Male patients must refrain from sperm donation from the initiation of the study and until at least 90 days after the last dose of investigational product.
 5. Must provide written informed consent and agree to comply with the study protocol.

Key Exclusion Criteria:

1. Any history or presence in the last 30 days, before rolling over to this study, of other concomitant liver diseases, including any of the following:
 - Hepatitis C virus (HCV) infection with positive RNA
 - Active hepatitis B virus (HBV) infection; however, subjects who have seroconverted (hepatitis B surface antigen negative [sAg-], hepatitis B surface antibody positive [sAB+]; hepatitis B e-antigen negative [eAg-], hepatitis B e-antibody positive [eAb+]; HBV DNA negative) may be included in this study after consultation with the Medical Monitor and Sponsor Medical Monitor
 - Subjects should be excluded if positive HBV DNA or HCV RNA
 - Primary sclerosing cholangitis
 - Alcoholic liver disease
 - Definite autoimmune liver disease or PBC-autoimmune hepatitis (AIH) overlap
 - Metabolic dysfunction-associated steatohepatitis (MASH)
 - Gilbert's Syndrome (due to interpretability of bilirubin levels)
 - Rare liver conditions such as Wilson's disease, hemochromatosis, alpha-one anti-trypsin deficiency, or other conditions identified by the Principal Investigator
2. Clinical complications of PBC including:
 - Prior liver transplantation
3. Any history or presence in the last 30 days, before rolling over to this study, of any one of the following decompensating events:
 - Child-Pugh (CP) Score ≥ 7

- Clinical evidence of decompensated liver disease or evidence of portal hypertension, including but not limited to:
 - Varices (including a history of esophageal varix ligation or asymptomatic esophageal varices by endoscopy)
 - Ascites/hepatic hydrothorax
 - Spontaneous bacterial peritonitis
 - Hepatic encephalopathy
 - Jaundice (with total bilirubin >3 mg/dL [$>51.3 \mu\text{mol/L}$])
 - Biochemical evidence of hepatic impairment, decompensation, or injury including at least one of the following:
 - Total bilirubin >ULN

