5.4.3. Obeticholic Acid and Bezafibrate in Combination

Results from Phase 2 studies (Studies 747-213 and 747-214) demonstrated that OCA in combination with BZF provides substantial improvements in key biochemical markers. At Week 12, the greatest reductions in ALP were observed in the OCA + BZF 400 mg treatment groups, with an increase in treatment effect with the addition of OCA compared to BZF 400 mg alone. In Study 747-213, treatment with OCA 5-10 mg + BZF 400 mg SR resulted in least square (LS) mean absolute reduction in ALP of 196.4 U/L (62.3%) compared to a 134.2 U/L

(45.1%) reduction in the Placebo + BZF 400 mg SR active comparator arm. In Study 747-214, treatment with OCA 5 mg + BZF 400 mg immediate release (IR) resulted in a LS mean absolute reduction in ALP of 183.1 U/L (61.4%) compared to a 164.2 U/L (54.2%) reduction in the Placebo + BZF 400 mg IR active comparator arm.

Safety data from Phase 1 Study 747-123 and the first 6 months of Phase 2 Studies 747-213 and 747-214 indicated that OCA + BZF was generally well tolerated. The majority of treatment-emergent adverse events (TEAEs) were mild to moderate in severity. No SAEs have been reported in Study 747-123. In the first 6 months Study 747-213, three SAEs were reported (hypertension, pruritus, and breast cancer). In the first 6 months of Study 747-214 three SAEs were reported (pneumonia, basal cell carcinoma, and intraductal proliferative breast lesion). No TEAEs leading to death have been reported across the 3 studies.

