7.1.2. Study Design Diagram

Figure 1: Study Design Schematic

BZF=bezafibrate; D=day; EOS=end of study; FDC=fixed-dose combination; IP=investigational product; LTSE=long-term safety extension; M=month; OCA=obeticholic acid; SR=sustained release; UDCA=ursodeoxycholic acid

Notes: Subjects taking UDCA at the time of enrollment will remain on their stable dose of UDCA during the study.

Subjects will be re-consented.

Subjects in either Study 747-213 or Study 747-214 may already be in LTSE. The time subjects spent in LTSE on either study will not be carried over into this study, 977-311. Subjects will spend a total of 60 months (5 years) in Study 977-311.

^a The Day 2 Visit can be either a virtual or onsite visit. It will be scheduled on Day 2 to Day 7 of the study depending on when laboratory results are available and reviewed. Subjects can elect to pickup IP onsite (onsite Day 2 visit) or have it shipped directly to them (virtual Day 2 visit). For subjects that have IP shipped, the Day 2 virtual visit should be scheduled once the subject receives IP.

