8.2. Subject Inclusion Criteria

1. All subjects with PBC who participated and are actively taking investigational product in Study 747-213 or Study 747-214 (or other Sponsor studies) are eligible to enroll in this study (977-311).

- Subjects on a drug holiday within the previous 60 days due to unresolved TEAEs or SAEs in the parent study should discuss eligibility for rolling over to this study with the Sponsor Medical Monitor.
2. Contraception: Female subjects must be postmenopausal, surgically sterile, or, if premenopausal (and not surgically sterile), be prepared to use ≥ 1 highly effective method of contraception during the study and for at least 30 days after the last dose of investigational product. Highly effective methods of contraception per the Clinical Trials Facilitation and Coordination Group guidelines are those that alone or in combination results in a failure rate of less than 1% per year when used consistently and correctly. These highly effective contraception methods avoid the potential embryofetal risks from exposure to investigational medicinal products. Highly effective methods of contraception are as follows:
- Intrauterine device
 - Intrauterine device
 - Intrauterine hormone-releasing system
 - Bilateral tubal occlusion
 - Vasectomy (partner)
 - Combined (estrogen and progestogen containing) hormonal contraception (e.g., oral, intravaginal or transdermal) associated with inhibition of ovulation. If oral contraceptives are used, they must be used in combination with a male or female condom. Female subjects should have been on the hormone contraception for at least 8 days prior to Day 1 of their parent study.
 - Progestogen-only hormonal contraception (e.g., oral, injectable, or implantable) associated with inhibition of ovulation. If oral contraceptives are used, they must be used in combination with a male or female condom. Female subjects should have been on the hormone contraception for at least 8 days prior to Day 1 of their parent study.
 - Sexual abstinence, as a form of highly effective contraception if in line with the preferred and usual lifestyle of the subject, is defined as avoiding all types of sexual activity that could result in pregnancy during the entire period of the study treatment until at least 30 days after the last dose of investigational product. The reliability of sexual abstinence needs to be evaluated in relation to the duration of the clinical study.

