5.1. Baseline Definitions

The Baseline value for statistical analyses is defined as the last evaluations prior to the first administration of investigational product in Study 977-311, unless otherwise specified. For subjects under protocol amendment 2, the baseline value is defined as the evaluations on Day 1.

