9.5. Subgroup Analyses of Efficacy

No subgroup analysis of efficacy is planned in this study.

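### The ≥40% and ≥15% ALP reduction rules are measured only from the on-treatment value at entry to 977-311, so a response that is fully kept is scored as no response

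*SAP*

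**What the plan says.** SAP 9.1 (Efficacy Endpoints) fixes the efficacy baseline: "Baseline is defined as the last assessment performed before the first dose of investigational product in Study 977-311, unless otherwise specified". Protocol 15.4 has the same rule. SAP 5.1 gives the same default and adds: "For subjects under protocol amendment 2, the baseline value is defined as the evaluations on Day 1". All three point to entry into 977-311.

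Three SAP 9.1 endpoints use that baseline for ALP: the rate of ≥40% reduction; the composite of ALP below 1.67×ULN, total bilirubin at or below ULN and an ALP decrease of ≥15%; and change from baseline. ALP normalization is listed beside the 40% rate but is judged against the normal range in SAP 10.3 (upper limit 122 U/L).

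Protocol 8.2, criterion 1, admits subjects with PBC "who participated and are actively taking investigational product in Study 747-213 or Study 747-214", or in other Sponsor studies. Those on a recent drug holiday for unresolved events are referred to the Sponsor Medical Monitor. No washout is described. Protocol 7.1.2 notes: "Subjects in either Study 747-213 or Study 747-214 may already be in LTSE".

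No readable text uses the phrase about other specification to supply a parent-study baseline for efficacy. Protocol 15.3.2 and SAP 10.3 do define baseline as a mean of all evaluations before treatment, but both sit in the safety laboratory sections and neither names a parent-study value.

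**The concern.** A percentage-reduction rule asks how far ALP has fallen since before the drug acted. Here most of that fall is expected to have happened before the reference value is taken. Protocol 5.4.3 reports Week 12 ALP reductions of 61–62% on OCA + BZF 400 mg and 45–54% on BZF 400 mg alone, all before rollover.

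At stake is how two response rates would be read. A subject with sustained control counts against the drug, while a subject who enters on a weaker regimen, or just after a drug holiday, can count as a responder. A low tabulated response rate could then be taken as poor efficacy when it partly records how well subjects were controlled on entry.

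**Working it through.** The plan gives no figure to reproduce: there is no hypothesis, and the sample size of about 133 is set by rollover. The check applies the SAP's scoring rules to the protocol's own numbers.

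**Inputs**
- Percentage change = (post-baseline − baseline) / baseline × 100 (SAP 5.4).
- Thresholds: ≥40% and ≥15% reduction (SAP 9.1).
- ALP ULN 122 U/L (SAP 10.3), so 1.67×ULN = 203.7 U/L.
- Week 12 LS mean ALP reductions (Protocol 5.4.3): 747-213 combination (OCA 5–10 mg + BZF 400 mg SR) 196.4 U/L, 62.3%, and BZF 400 mg SR alone 45.1%; 747-214 combination (OCA 5 mg + BZF 400 mg IR) 183.1 U/L, 61.4%, and BZF 400 mg IR alone 54.2%.

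**Step 1. Stable responder.** If ALP at a visit equals ALP at entry, the change is 0%. Since 0% is below both 15% and 40%, the subject fails both rules at any ALP level. This step needs no estimate.

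**Step 2. Implied ALP levels.** Pre-treatment ALP ≈ absolute reduction / fractional reduction, and on-treatment ALP is that value minus the reduction.
- 747-213 combination: 196.4 / 0.623 = 315.2; 315.2 − 196.4 = 118.8 U/L.
- 747-214 combination: 183.1 / 0.614 = 298.2; 298.2 − 183.1 = 115.1 U/L.

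**Step 3. What such a subject needs in order to score.** With r the reduction already reached at entry and d the threshold, total reduction needed = 1 − (1 − r)(1 − d).

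| Combination arm | 40% rule: ALP needed | 40% rule: total reduction | 15% rule: ALP needed | 15% rule: total reduction |
|---|---|---|---|---|
| 747-213 | 0.60 × 118.8 = 71.3 U/L | 1 − 0.377 × 0.60 = 77.4% | 0.85 × 118.8 = 101.0 U/L | 1 − 0.377 × 0.85 = 68.0% |
| 747-214 | 0.60 × 115.1 = 69.1 U/L | 1 − 0.386 × 0.60 = 76.8% | 0.85 × 115.1 = 97.8 U/L | 1 − 0.386 × 0.85 = 67.2% |

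**Step 4. Subject moving from BZF 400 mg alone to the full combination effect.** Fall from rollover = 1 − (fraction remaining on combination) / (fraction remaining on BZF alone).
- 747-213: 1 − 0.377 / 0.549 = 31.3%.
- 747-214: 1 − 0.386 / 0.458 = 15.7%.

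Both miss 40%. Both pass 15%, the second only just.

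**Step 5. Same stable combination subject, parent-study pre-treatment baseline.** The reduction is 62.3% or 61.4%, so the 40% and 15% rules are met. The implied ALP of about 119 or 115 U/L is below 203.7, so both ALP parts of the composite are met.

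**Step 6. Measurement noise (illustration on an assumed input).** The documents give no within-subject variability. Assume a truly stable subject and a within-subject CV of 10% to 25%, taken as the SD of log ALP. The SD of the log ratio of two readings is CV × √2. The chance of an apparent ≥40% fall is Φ(ln 0.60 / (CV√2)) = 0.02% to 7.4%. For ≥15% it is Φ(ln 0.85 / (CV√2)) = 12.5% to 32%. So the 15% component would not read zero even in stable subjects, but the passes would be chance.

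**The case against.** The strongest reply is that the entry baseline suits this study's purpose. The primary objective is safety. The efficacy objective concerns the FDC tablet, which starts at rollover, and SAP 9.1 plans no inference on these endpoints. A change near zero is then a valid maintenance result, and the entry baseline is the right one for detecting later loss of effect. All of this stands, and it is why the entry baseline should be kept. It does not rescue the two threshold rules, which record a maintained response as a failure.

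Several stronger readings are tempting, and the documents do not support them:

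- *That the study cannot answer its efficacy objective.* ALP values are summarized at baseline and every visit, and normalization and the 1.67×ULN limit are absolute. Maintained control would be visible there.
- *That the composite rate would be near zero.* Step 4 shows average BZF-alone switchers passing 15%. Parent regimens also included OCA alone and BZF 100 or 200 mg, and other Sponsor studies may contribute. With the mix unknown, no trial-level rate follows.
- *That any non-zero change reflects prior regimen.* Over 60 months, change can also come from progression, less frequent dosing, or discontinuation, which the treatment-policy approach includes.
- *That bilirubin normalization is empty because "Total bilirubin >ULN" is an exclusion.* The first subject enrolled in July 2024, before Version 2.0 of 18 November 2024. The summary of changes shows that Version 1.0 set this biochemical limit at 3 mg/dL. Out-of-range Day 1 results are reviewed case by case, and the SAP does not restrict the denominator to subjects abnormal at baseline.

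Making the parent-study value the main baseline would also be open to challenge. It would credit the FDC with response gained on other regimens, in subjects selected for having tolerated treatment until rollover. A split by prior regimen is a reasonable request, but "No subgroup analysis of efficacy is planned in this study" is a stated choice with about 133 subjects.

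**Conclusion.** The point holds for three ALP outputs. The ≥40% response rate and the ≥15% component of the composite cannot register a response achieved before entry and kept, and ALP change from baseline shows only change since rollover. ALP normalization, the absolute limits within the composite and values by visit are unaffected.

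The stable-responder result is logical and rests on no estimate. The sizes (about 77% total reduction for the 40% rule, 67–68% for the 15% rule, and falls of 31% or 16% for switchers) are approximate. They treat the LS mean percentage as an average subject's reduction and assume the Week 12 level is held until rollover. The U/L levels further assume that the absolute and percentage LS means share one baseline. They lie so close to 122 U/L that nothing should rest on which side of ULN they fall. How many of about 133 subjects would be misclassified cannot be computed.

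This is a should-fix: the endpoints are descriptive and not primary, but the 15% composite is a named efficacy objective and the remedy is simple.

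**What to change.** In SAP 9.1, for subjects first treated in a parent study:

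1. Also compute the ≥40% ALP response, the composite and ALP change from the parent-study pre-treatment baseline.
2. Keep the 977-311 entry baseline for the same outputs, labelled as change since rollover (maintenance).
3. State with the tables that responses from the parent-study baseline include effect gained on parent-study regimens, in subjects selected for tolerating treatment until rollover.

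The cost is SAP wording, linkage to parent-study data that the sponsor already holds, and extra table columns. No new visits or samples are needed. SAP section 1 has the plan finalized before database lock. Protocol section 15 asks for it before any study snapshot, so the change should be made before the first data cut.
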